10.3 Cytarabine

Product description: Antimetabolite. Commercially available in 100 mg, 500 mg, 1 gm, and 2 gm vials.

Solution preparation: For IV use, reconstitute the 100 mg vial with 5 mL bacteriostatic water for injection to achieve a concentration of 20 mg/mL. Add 10 mL of bacteriostatic water to the 500 mg vial to achieve a final concentration of 50 mg/mL. Add 10 and 20 mL of bacteriostatic water to the 1 and 2 gm vials respectively to achieve a final concentration of 100 mg/mL.

Storage and stability: The dry powder is stored at room temperature. Solutions reconstituted with sterile water without preservative should be used immediately; solutions reconstituted with Bacteriostatic of Water are stable up to 48 hours at controlled room temperature (15° to 30°C). Solutions with a slight haze should be discarded.

Route of administration: Continuous intravenous infusion over 24 hours.

Disposal: Care should be taken in disposing cytarabine. Dispose of per local regulations and the Wake Forest Hem/Onc Waste Disposal Guide.

12.0 Data Management

Informed consent document	ORIS
Protocol registration form	ORIS
Subject Eligibility	ORIS
Treatment response form (Appendix D)	REDCap
Cardiac function worksheet (Appendix E)	REDCap
Adverse events log (Appendix F)	ORIS

13.0 Statistical Considerations

13.1 Analysis of Primary Objective

Since this is a pilot study, several descriptive analyses will be performed. These will include examining the change in each measure of cardiotoxicity from the initial pre-chemotherapy assessment to each of the available post-chemotherapy imaging assessment (i.e. EF, LVEDV, LVESV, T1/T2 mapping, myocardial strain). These comparisons will be made using paired T-tests. Similar analyses will be performed using the ECHO-derived measures. In addition to examining the continuous changes in measures, we will determine the proportion of patients who exhibit a cardio-toxic event at 3-months defined as have a reduction in LVEF \geq 10% and EF \leq 50% when compared to baseline. This event will be defined for both the ECHO and MRI measures. In addition to point estimates of these rates, 95% confidence intervals will be calculated.

Additional toxicity measures will be tabulated after each visit.

CYTARABINE PLUS CONTINUOUS INFUSION DAUNORUBICIN, WITH CARDIAC
MRI MONITORING, INDUCTION THERAPY FOR ADULTS WITH ACUTE MYELOID
LEUKEMIA; A FEASIBILITY STUDY

Wake Forest Baptist Comprehensive Cancer Center (WFBCCC) CCCWFU 22616

For feasibility assessment, we will determine the proportion of patients with study-related deviations and report these proportions with 95% confidence intervals. In addition, we will determine the proportion of patients who complete the infusion therapy.

13.2 Analysis of Secondary Objective

Similar toxicity analyses as described above for the primary objective will be examined at the 6-month time point.

We will report frequencies of response status (Overall response rate [CR + CRI]; Induction death rate; Percentage of patients with persistent leukemia; Disease-free survival [for those who achieve remission]) with the number of patients in each category of response. Treatment outcomes will be stratified by age (≥ 60 , < 60), ECOG (0-2, 3), cytogenetic risk groups and prior hematological disease (e.g. MDS, MPN).

Three sets of correlation analyses will be performed; the first will determine the correlation between ECHO and MRI assessments performed pre-chemotherapy; the second will assess correlations between post-chemotherapy ECHO and MRI assessments; and the third will assess correlations between each of the time points. In addition to the correlation analyses, paired t-tests will be performed to compare the actual values of each ECHO/MRI measurement to each other at each time point. Finally, Bland-Altman plots will be generated at baseline, follow-up and using the change in measure for each of the MRI/ECHO derived measures.

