2.2 Secondary Objectives

- 2.2.1 To assess the safety (at 6 months) of administering daunorubicin as continuous infusion under the proposed treatment regimen.
- 2.2.2 To assess treatment outcomes (including CR and CRi) in patients with AML under the proposed treatment regimen.
- 2.2.3 To compare the concordance between MRI and ECHO in identifying cardiac toxicity, i.e. a reduction in LVEF of $\geq 10\%$ and $EF \leq 50\%$ compared to baseline LVEF.

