5.0 Study Outcomes

5.1 Primary Outcomes

- 5.1.1 Cardiac toxicity(see 2.2.3), as measured by MRI (ejection fraction [EF], left ventricular end diastolic volume [LVEDV], left ventricular end systolic volume [LVESV], T1/T2 mapping and myocardial strain) measures and ECHO (EF, myocardial strain, LVEDV, LVESV, ESV, mitral inflow E, A, E' and A') measures. Cardiac toxicity is defined as reduction in LVEF of $\geq 10\%$ compared to baseline LVEF and $EF \leq 50\%$ on the follow-up scan. This assessment will be performed using both an ECHO and MRI measure. In addition, the primary outcome will be assessed at the 3 month follow-up (or relapse) visit.
- 5.1.2 Other unexpected toxicities (exclude hematologic and infectious) \geq grade 3, as measured by CTCAE v 4.0
- 5.1.3 Feasibility, as measured by ability to administer continuous infusion daunorubicin and complete required study assessments with limited deviation from the proposed regimen (as defined in section 8.2)

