6.6 Duration of Follow Up

Patients will have an MRI without contrast and full/limited ECHO at 3 months or relapse, whichever occurs first. Patients still on protocol at 6 months post-treatment will have an MRI without contrast only.

Patients will be followed for a minimum of 30 days after the last study drug is administered or until death, whichever occurs first, for adverse events monitoring. Patients removed from the study for unacceptable adverse events will be followed until resolution or stabilization of the adverse event.

CYTARABINE PLUS CONTINUOUS INFUSION DAUNORUBICIN, WITH CARDIAC
MRI MONITORING, INDUCTION THERAPY FOR ADULTS WITH ACUTE MYELOID
LEUKEMIA; A FEASIBILITY STUDY

Wake Forest Baptist Comprehensive Cancer Center (WFBCCC) CCCWFU 22616

Patients will be followed by phone call every 3 months for monitoring survival endpoints.

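### Objective 2.2.3 asks whether MRI and ECHO agree on who has cardiac toxicity, but no planned analysis cross-classifies the two yes/no calls

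*Combined protocol and SAP*

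**What the plan says.** Section 2.2, objective 2.2.3, is "To compare the concordance between MRI and ECHO in identifying cardiac toxicity", followed by the definition of toxicity as an LVEF fall of at least 10% with EF at or below 50%.

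Section 5.1.1 refers back to that objective ("Cardiac toxicity(see 2.2.3), as measured by MRI") and has each modality make its own call: "This assessment will be performed using both an ECHO and MRI measure".

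Section 13.1 takes the proportion of patients with the event at 3 months. It says "This event will be defined for both the ECHO and MRI measures" and "In addition to point estimates of these rates, 95% confidence intervals will be calculated". The result is two separate rates.

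Section 13.2 holds the comparison of the modalities. It plans three sets of correlations, then "paired t-tests will be performed to compare the actual values of each ECHO/MRI measurement to each other at each time point", and finally "Bland-Altman plots will be generated at baseline, follow-up and using the change in measure for each of the MRI/ECHO derived measures". Outcome 5.2.3, which pairs the modalities, lists only EF, strain and volumes.

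On timing, section 6.6 says "Patients will have an MRI without contrast and full/limited ECHO at 3 months or relapse, whichever occurs first" and leaves MRI alone at 6 months. Appendix E marks ECHO as not applicable at 6 months.

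**The concern.** The objective asks whether two imaging methods identify the same patients. That is a question about paired binary classifications, and it needs the joint distribution of the two calls. The plan gives the two marginal rates and, separately, the agreement of the continuous measurements. Neither is the joint distribution.

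Section 1.2 names the use of cardiac MRI in detecting cardiac toxicity as something the study will examine. Followed to the letter, the plan would produce a report that does not say whether a patient flagged by MRI was also flagged by ECHO. If the table were added only after the data were seen, the reading of the 10% fall could then also be chosen with the results in view.

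**Working it through.** **The plan's own figures.** Section 13.3 gives a detectable difference of 0.511 SD at n = 32 (recomputed from the noncentral t: 0.5113) and a precision of ±0.181 for the 3-month rate (the Clopper-Pearson half-width at 16/32 is 0.1811). Both reproduce. The first concerns a paired mean difference and the second a single rate; neither concerns concordance.

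**Step 1: the separate rates do not fix the overlap.** Inputs: n = 32 evaluable patients (section 13.3) and, as an assumption, 4 events on each modality. Let *s* be the number flagged by both. The 2x2 counts (both / ECHO only / MRI only / neither) are *s*, 4−*s*, 4−*s*, 24+*s*.

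- Overall agreement: p_o = (24 + 2*s*)/32
- Chance agreement: p_e = (4/32)² + (28/32)² = 0.0156 + 0.7656 = 0.781
- Kappa = (p_o − p_e)/(1 − p_e)
- Positive agreement = 2*s*/8

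| Shared *s* | Discordant | Agreement (exact 95% CI) | Positive agreement | Kappa |
|---|---|---|---|---|
| 0 | 8 | 0.750 (0.566 to 0.885) | 0 | -0.143 |
| 1 | 6 | 0.813 (0.636 to 0.928) | 0.25 | 0.143 |
| 2 | 4 | 0.875 (0.710 to 0.965) | 0.50 | 0.429 |
| 3 | 2 | 0.938 (0.792 to 0.992) | 0.75 | 0.714 |
| 4 | 0 | 1.000 (0.891 to 1.000) | 1.00 | 1.000 |

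In every row section 13.1 reports the same thing: 12.5% (95% CI 3.5% to 29.0%) for each modality. With 2, 6 or 8 events on each modality, kappa at zero overlap is -0.067, -0.231 or -0.333, and the maximum is still 1.00.

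**Step 2: the continuous comparisons do not fix it either.** A call depends on a patient's change and on that same patient's follow-up EF. The separate plots do not link the two. Take three patients, with values written as (ECHO EF, MRI EF):

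| Baseline | Follow-up in set A | Flagged in A | Follow-up in set B | Flagged in B |
|---|---|---|---|---|
| (54, 61) | (53, 58) | neither | (42, 47) | both |
| (52, 51) | (42, 47) | ECHO only | (51, 48) | neither |
| (63, 62) | (51, 48) | MRI only | (53, 58) | neither |

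Both sets contain the same baseline pairs, the same follow-up pairs and the same change pairs: (-1, -3), (-10, -4) and (-12, -14). Four such triples plus the same 20 unflagged patients make n = 32 with 4 events on each modality.

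A numerical check confirms that A and B share:
- ECHO-MRI correlations, mean differences, limits of agreement and paired t statistics at baseline, at follow-up and for change;
- within-modality t statistics and Pearson correlations over time.

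The 2x2 table is nevertheless 0/4/4/24 in A (kappa -0.143) and 4/0/0/28 in B (kappa 1.00), whether the 10% fall is read as relative or as absolute points.

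**Step 3: the reading of the 10% fall matters to the calls.** Combined with EF ≤ 50, the follow-up cut-off is min(50, 0.9 × baseline) on the relative reading and min(50, baseline − 10) on the absolute one. From baseline 60 upward both are 50. Below 60 they part: baseline 58 gives 50 against 48; 55 gives 49.5 against 45; and 45, the ECHO eligibility floor in section 3.1.4, gives 40.5 against 35.

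**The case against.** The best defence is that section 13.2 already gives the comparison a full paragraph. EF and its change are the only inputs to the call, Bland-Altman is a standard agreement method, and with about 32 pairs continuous agreement carries more information than a dichotomised call. This is a descriptive pilot, and the table could be made at reporting without new data. Much of that stands: the objective is partly served, no data are lost, and the plots should stay. But agreement in EF is not agreement in who is flagged, and the objective is worded in terms of the latter.

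It is also fair that the extremes above are bounds. Zero overlap between two measurements of the same ventricle is improbable, and the example was built to hold the planned outputs constant. It shows what is possible, not what is likely. Nor does it hold every conceivable output constant. Rank correlations within a modality over time would differ between A and B, as would correlations of one modality at baseline with the other at follow-up, which the third correlation set in section 13.2 might be read to include. None of these reports the calls.

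Finally, kappa will be imprecise. With 4 events on each modality and 2 shared, the approximate 95% CI is -0.04 to 0.89; with 3 shared it is 0.34 to 1.09, beyond the possible range. That argues for leading with counts, not for omitting the table.

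**Conclusion.** The concern holds. A named secondary objective about concordance of a binary call has no analysis of that call; the plan covers only the separate rates and the underlying continuous measures. This conclusion rests on the text. The arithmetic shows only that the planned outputs need not reveal the answer: at an assumed 4/32 on each modality, overall agreement may be 75% to 100% and kappa -0.14 to 1.00 with identical reported rates. The consequence is confined to objective 2.2.3. It should be corrected because the remedy costs almost nothing, but no primary result, sample-size figure or safety decision changes.

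**What to change.** Add to section 13.2 a paired 2x2 table of ECHO call by MRI call at the 3-month (or relapse) visit, using the section 13.1 event definition, in patients with EF by both modalities at baseline and at that visit. Make the four counts the main display. Beside them give overall agreement with an exact 95% CI, positive and negative agreement, and Cohen's kappa with a 95% CI, all labelled descriptive. If either modality has no events, show counts only.

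Three points should go with it:
- State one reading of the 10% fall, relative or absolute, and apply it to both modalities, or show the table under both readings.
- Limit the table to 3 months or relapse, since section 6.6 and Appendix E have no ECHO at 6 months. Outcome 5.2.1 speaks of both modalities at 6 months and should be reconciled with them.
- Note that baseline ECHO is full 3D while Appendix E specifies a limited ECHO at follow-up (section 6.6 says full or limited), so some discordance may reflect technique.

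Keep the Bland-Altman plots as supportive. Rewording outcome 5.2.3 is optional.

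The cost is one table and a few sentences, from EF values already collected, with no new scan or visit. The drawback is wide intervals when events are few.

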13.3 Power and Sample Size

Assuming a sample size of 32 evaluable patients (assuming a drop rate of up to 20% by 3-months) we will need to enroll 40 total patients. With $n=32$ patients, we have 80% power to detect a 0.511 standard deviation difference using a paired t-test assuming $\alpha=0.05$ (2-sided). If the drop-out rate is lower (i.e., $n=40$) then the detectable difference would be 0.45 standard deviations. This difference should demonstrate a meaningful change in the cardiotoxic parameters of interest. In addition, with $n=32$ patients we can estimate the 3-month cardio-toxicity rate within $+- 0.181$ using an 95% Exact Clopper-Pearson 2-sided confidence interval.

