1.0 Introduction and Background

It is estimated that 19,950 people will be diagnosed with acute myeloid leukemia (AML) and 10,430 will die from it in the United States in 2016.¹ Standard induction therapy for patients with good performance status consists of a 7+3 regimen of cytarabine 100-200 mg/m² continuous infusion x 7 days with an anthracycline, i.e. daunorubicin 60-90 mg/m² (45-90 mg/m² for patients \geq 60 years or idarubicin 12 mg/m²) x 3 days.² While advances in treatment have resulted in substantially improved complete remission (CR) rates, with 60% to 70% of adults expected to attain CR status following appropriate induction therapy, only slightly more than 25% (about 45% of those who attain CR) can be expected to survive 3 or more years.

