6.1 Treatment Administration

Treatment will be administered on an inpatient basis. Reported adverse events and potential risks are described in Section 9. No investigational or commercial agents or therapies other than those described below may be administered with the intent to treat the patient's malignancy.

Agent	Dose	Route	Schedule	Cycle Length
Induction				
Cytarabine	100 mg/m ² /day	IV infusion	Days 1-7	14 days
Daunorubicin	60 mg/m ² /day	IV infusion	Days 1-3	
Re-induction (if needed)				
Cytarabine	100 mg/m ² /day	IV infusion	Days 1-5	14 days
Daunorubicin	60 mg/m ² /day	IV infusion	Days 1-2	
Consolidation (up to 3 cycles, or up to 4 cycles for CBF AML)				
Cytarabine	<60 yrs: 3,000 mg/m ² /day ≥ 60 yrs: 1,500 mg/m ² /day	IV infusion over 3 hours, every 12 hours	Days 1,3,5	≥ 28 days

Induction: This study regimen will follow the standard 7+3 regimen of cytarabine and daunorubicin, with the modification of daunorubicin administered as continuous infusion rather than bolus. Baseline troponin I, full 3D ECHO, and MRI without contrast will be performed prior to treatment.

For troponin determination, the study will use either the TnI-Ultra™ assay, Siemens, Munich Germany or the Beckman Coulter Access 2 AccuTnI+3 assay for detection of troponin I. While the assays are comparable, every effort will be made to test all samples on the current Institutional standard troponin I testing platform (TnI-Ultra assay, Siemens). If the TnI-Ultra assay becomes unavailable either because of changing Institutional standards or product availability the Beckman Coulter Access 2 AccuTnI+3 assay will be utilized. The brand of assay and results will be recorded for each test on the Cardiac Function Worksheet.

Patients will have a bone marrow aspirate and biopsy on day 14 (± 2 days).

Re-induction: A second induction course may be given if the day 14 bone marrow aspirate and biopsy shows bone marrow cellularity as $\geq 10\%$ and $> 5\%$ leukemic blasts. Those requiring re-induction will undergo a limited ECHO with strain measures prior to treatment. This abbreviated cycle will consist of cytarabine on days 1-5 and daunorubicin on days 1 and 2, with a troponin I measure on day 3 and a bone marrow biopsy on day 14 (± 2 days). Patients not achieving a remission after 2 induction attempts will be removed from study.

CYTARABINE PLUS CONTINUOUS INFUSION DAUNORUBICIN, WITH CARDIAC
MRI MONITORING, INDUCTION THERAPY FOR ADULTS WITH ACUTE MYELOID

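### The 20% loss that turns 40 enrolled into 32 evaluable in section 13.3 is not supported by the protocol's own remission rate, removal rule and imaging schedule

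*Combined protocol and SAP*

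**What the plan says.** Section 13.3 starts from 32 evaluable patients, allows for loss ("assuming a drop rate of up to 20% by 3-months"), and concludes that "we will need to enroll 40 total patients". For n=32 it states that "we have 80% power to detect a 0.511 standard deviation difference using a paired t-test" at two-sided alpha 0.05, and that the 3-month cardiotoxicity rate can be estimated to within ±0.181 by an exact 95% interval. The only other case shown is full retention, n=40: "then the detectable difference would be 0.45 standard deviations". No source or breakdown is given for the 20%.

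Four other places bear on how many patients reach the 3-month assessment:

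- Section 1.0 describes standard induction "with 60% to 70% of adults expected to attain CR status following appropriate induction therapy". Section 1.2 expects response with continuous infusion to be at least similar.
- Section 6.1 says: "Patients not achieving a remission after 2 induction attempts will be removed from study". Section 8.2 repeats the rule in its definition of persistent leukemia.
- Section 6.6 and Appendix E schedule post-treatment imaging at 3 months or relapse, and at 6 months. Neither names a scan at removal for non-remission.
- Sections 5.2.2 and 13.2 count CR and CRi together as response.

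**The concern.** The paired t-tests and the 3-month event rate in section 13.1 both need a baseline and a 3-month scan. The loss that matters is therefore everything that prevents the 3-month scan: death, removal, withdrawal and missed or failed imaging. The protocol's own CR figure puts 30-40% of patients outside CR. Some of these die during induction. Those without remission after a second course are removed from study. A patient who never remits also has no relapse to trigger the alternative scan, since section 8.2 speaks of relapse from CR.

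If those patients are not scanned, the loss exceeds 20% before any other cause is counted. The 80% power, the 0.511 SD and the ±0.181 are the main justification for enrolling 40. The only alternative shown, n=40, is more favourable, and no less favourable case appears.

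**Working it through.** **Inputs.** From 13.3: 40 enrolled, 32 evaluable, 20% loss, paired t-test, two-sided alpha 0.05, 0.511 SD, 0.45 SD at n=40, ±0.181. From 1.0: CR 60-70%. Assumed, not in the documents: CRi adds 5-10 points to CR.

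**Formulas.**
- Enrolment = evaluable / (1 − loss).
- Power = P(T > t₀.₉₇₅,ₙ₋₁), where T is noncentral t with n − 1 degrees of freedom and noncentrality d√n, and d is in SDs of the paired difference. The detectable difference is the d that gives 80%.
- Half-width = half the length of the Clopper-Pearson 95% interval, maximised over all event counts.

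**Step 1: reproduce the plan.** 32 / 0.80 = 40. At n=32 the detectable difference is 0.5113 SD, power at 0.511 SD is 0.7996, and the maximum half-width is 0.1811 (at 16/32). At n=40 the detectable difference is 0.4543 SD. Every stated figure reproduces.

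**Step 2: evaluable patients if those without remission are not scanned and nobody else is lost.**
- Only CR counts as remission: 40 × 0.60 = 24, and 40 × 0.70 = 28.
- CRi also counts, adding 5-10 points: 40 × (0.60 + 0.05) = 26, and 40 × (0.70 + 0.10) = 32.

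**Step 3: consequences.**

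| n | Detectable at 80% power (SD) | Power at 0.511 SD | Maximum half-width |
|---|---|---|---|
| 32 | 0.511 | 80.0% | 0.181 |
| 28 | 0.549 | 74.1% | 0.194 |
| 26 | 0.572 | 70.7% | 0.201 |
| 24 | 0.597 | 66.9% | 0.209 |

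**Step 4: chance of reaching 32.** If each of 40 patients is evaluable with probability p, P(at least 32) is 0.6% at p=0.60, 3.0% at 0.65, 11.1% at 0.70, 30.0% at 0.75 and 59.3% at 0.80.

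**Step 5: break-even.** A 20% loss is 8 of 40. Patients outside CR number 12 (30%) to 16 (40%). The allowance holds only if no more than 8/12 (two thirds) or 8/16 (one half) of them miss the scan and nobody else is lost.

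**Step 6: where precision is affected.** The ±0.181 is the largest half-width over all event rates. At n=24 the half-width is 0.130 for 2 events, 0.175 for 5 events (21%) and 0.185 for 6 events (25%). The stated bound is therefore still met at n=24 for observed rates up to about 20%.

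**The case against.** A reader might infer three stronger things that the documents do not support.

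- **That 13.3 is miscalculated.** It is not. Every figure follows from n=32 or n=40.
- **That the protocol expects 30-40% of this trial's patients to be non-remitters.** It does not say so. The 60-70% is a background CR rate for adults, while the removal rule turns on remission. Response in this trial is CR plus CRi, and the text does not say whether CRi counts as remission for removal. If it does and adds 10 points to a 70% CR rate, 32 is reached, with no other loss.
- **That removed patients certainly miss the 3-month scan.** No passage says this. Section 6.6 restricts only the 6-month MRI to patients remaining on protocol, and section 8.2 makes everyone evaluable for toxicity from the first daunorubicin treatment. If enough living non-remitters are scanned, 20% may hold. The documents give no induction death rate to settle it.

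The consequences are also bounded. Section 13.1 calls this a pilot with descriptive analyses, infusion completion as a feasibility measure does not need the 3-month scan, and precision worsens beyond ±0.181 only at higher event rates.

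All of this stands, and it makes the shortfall conditional. It does not supply a basis for the 20%. Counting CRi reaches 32 only at the top of the assumed range, and retaining 32 otherwise depends on scans of removed patients that the text does not clearly provide for. Withdrawals, deaths in remission and failed scans all add to the loss. Patients with ECOG 3 are eligible (3.1.3), while section 1.0 describes standard induction for good performance status, so the CR figure is not obviously pessimistic here.

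**Conclusion.** The concern holds as a mismatch between the attrition input in 13.3 and sections 1.0, 6.1, 8.2 and 6.6. It does not show that the trial will fall short. On the natural reading that removed patients and induction deaths have no 3-month scan, 24-28 of 40 are evaluable: power of 67-74% at 0.511 SD, 0.55-0.60 SD detectable, and a maximum half-width of 0.19-0.21. With CRi counted as remission and adding an assumed 5-10 points, the ranges are 26-32 patients, 71-80%, 0.51-0.57 SD and 0.18-0.20. Both ranges exclude all other losses. The effect on power is moderate and that on precision modest. Because these figures justify the sample size, they should be restated.

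**What to change.** In section 13.3:

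- Give power at 0.511 SD, the detectable difference and the maximum half-width across n=24 to 32, as in the table above.
- Present n=32 as conditional on living non-remitters being imaged at 3 months, or on CRi keeping enough patients on study, with no other loss in either case.
- Label ±0.181 as the maximum half-width at n=32.
- State the basis of the 20%.

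Reconcile sections 6.1 and 8.2 with 6.6 on whether patients removed for non-remission keep the 3-month imaging, and state whether CRi counts as remission for the removal rule.

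The cost is rewording and somewhat less favourable stated figures. Added enrolment is not needed. For reference, holding 32 evaluable would take 46 enrolled at 30% loss (32 / 0.70 = 45.7) or 54 at 40% (32 / 0.60 = 53.3), but reporting the range openly is enough for a pilot with descriptive aims.
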